- Treatment-related NCI Common Terminology Criteria for Adverse Events (CTCAE, version 5.0) Grade ≥ 3 non-hematological toxicity that does not respond to supportive therapy and lasts for longer than 48 hours, or;

- Treatment-related NCI CTCAE v5.0 Grade ≥ 3 hematological toxicity that does not respond to supportive therapy and lasts for longer than 48 hours.

Additionally, enrollment and additional dosing will be paused until Sponsor discussion with the site Investigator determines that enrollment and dosing may continue, if the following CTCAE v5.0 events occur at any time in the study:

- One Grade 4 or 5 related SAE;
- Two Grade 3 related SAEs

Subjects will undergo routine surgical procedure for removal of papilloma(s) during the screening period within 14 days prior to Day 0 dosing (papilloma removal and Day 0 dose may be performed same day if other eligibility criteria have been fulfilled). Biopsy tissue will be collected and sent to [REDACTED] for evaluation of secondary [REDACTED] endpoints. Archival tissue (slides or blocks) obtained within one year of the screening window may be used, or a biopsy conducted during routine surgery.

Status of disease during the trial will be monitored by the Investigator during laryngoscopy including documentation with Staging Assessment scores. If at any time during the trial, surgical removal (including laser) of papilloma is clinically indicated per PI judgement, the subject may undergo procedure for papilloma removal but this must be captured on the electronic case report form. Documentation of the Staging Assessment score prior to surgery is required, and explanation for requirement of surgical removal of papilloma must be documented.

Surgical interventions during the trial must be documented to include at a minimum, information about the appearance and location of tissue being removed and instruments used. Video/photographic documentation of laryngoscopy is required.

This trial will not utilize a Data Safety Monitoring Board. This is a single-arm, open-label trial. The Sponsor will have access to unblinded safety and tolerability data during the trial. At a minimum, the Sponsor's Medical Monitor will review reported adverse events quarterly.

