3.3 SECONDARY OBJECTIVE(S)

1. To evaluate the efficacy of INO-3107, as determined by the frequency of RRP surgical interventions in the year following the first dose of investigational product, compared to the frequency in the year prior to Day 0.
2. To evaluate the efficacy of INO-3107 as assessed by changes in the RRP Staging Assessment over time.
3. To evaluate the cellular immune response to INO-3107 when given IM, followed by EP.
4. To evaluate the immunogenicity of INO-3107 as assessed by pro-inflammatory and immunosuppressive elements in resected tumor tissue at study entry and, if available, at subsequent tissue resections.

5. To evaluate any potential association of microRNA (miRNA) profile with decreased frequency of RRP surgical intervention.

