4.2 EXCLUSION CRITERIA

Subjects Must Not:

1. Receive therapy directed towards RRP disease (other than surgery or ablation) including but not limited to anti-virals (including cidofovir), radiation, chemotherapy, anti-angiogenic therapy (including bevacizumab), prophylactic HPV vaccination (including Gardasil) as therapeutic intervention, or therapy with an experimental agent within 3 months prior to Day 0;
2. Have ongoing or recent (within one year) evidence of autoimmune disease that required treatment with systemic immunosuppressive treatments, with the exception of: vitiligo, childhood asthma that has resolved, type 1 diabetes, residual hypothyroidism that requires only hormone replacement, or psoriasis that does not require systemic treatment;
3. Have a diagnosis of immunodeficiency or treatment with systemic immunosuppressive therapy within 28 days prior to the first dose of trial treatment, including systemic corticosteroids;
4. Have a high risk of bleeding or require the use of anti-coagulants for management of a known bleeding diathesis;
5. Receive any live virus vaccine within 4 weeks prior to first dose of trial treatment or any non-live vaccine within two weeks prior to the first dose of trial treatment;
6. Have a history of clinically significant, medically unstable disease which, in the judgment of the Investigator, would jeopardize the safety of the subject, interfere with trial assessments or endpoint evaluation, or otherwise impact the validity of the trial results. This may include chronic renal failure; myocardial ischemia or infarction; New York Heart Association (NYHA) class III/ IV cardiac disease); any cardiac pre-excitation syndromes (such as Wolff-Parkinson-White; cardiomyopathy, or clinically significant arrhythmias); current malignancy with the exception of treated basal or squamous cell skin cancers, prostate cancer, or carcinoma of the cervix in situ; HIV, which may impact the ability to mount an immune response to the study therapy; or drug or alcohol dependence;
7. Have fewer than two acceptable sites available for IM injection considering the deltoid and anterolateral quadriceps muscles. The following are unacceptable sites:
 - a. Tattoos, keloids or hypertrophic scars located within 2 cm of intended treatment site;

- b. Cardioverter-defibrillator or pacemaker (to prevent a life-threatening arrhythmia) that is located ipsilateral to the deltoid injection site (unless deemed acceptable by a cardiologist);

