6.1.1 CLINICAL TRIAL SCREENING EVALUATIONS

The assessments performed during Screening will determine the subject's eligibility for the study and their ability to comply with protocol requirements by completing all screening assessments. Subjects' post-menopausal status must meet requirements as specified in the inclusion criteria. The following screening evaluations will be performed within 60 days prior to dosing on Day 0. All screening assessment values must be reviewed prior to the first Study IP administration.

If a subject does not meet an inclusion or exclusion criterion due to a transient and non-clinically significant event at Screening, relevant Screening evaluations may be repeated within the same 60-day Screening period. If the subject fails twice, they will be considered a screen failure.

- Signed and dated informed consent ([Section 6.2](#));
- Review and confirm all inclusion/exclusion criteria ([Section 4.1](#) and [4.2](#));
- Obtain and document complete medical history, surgical history (including all past procedures), present conditions and concomitant illnesses ([Section 6.1.1.1](#)); document all present and/or new or ongoing adverse events prior to administration of IP;
- Collect demographics ([Section 6.1.1.2](#));
- Smoking history ([Section 6.1.1.3](#));
- Full physical examinations ([Section 6.4.1](#));
- Record current concomitant medications/treatments ([Section 6.13](#));
- Record vital signs heart rate (HR), respiratory rate (RR), blood pressure (BP) and body temperature ([Section 6.4.2](#));
- Record body weight, height and determine BMI ([Section 6.4.3](#));
- Collect blood for screening laboratory evaluations ([Section 6.4.4](#));
- Collect blood for serum pregnancy test, if applicable ([Section 6.4.4](#));
- Collect whole blood [REDACTED] for immunology assessment ([Section 6.10](#));
- Perform laryngoscopy and Staging assessment ([Section 6.4.5](#)) prior to surgical removal of papilloma(s).
- Surgical removal of papilloma(s)
- Biopsy tissue (archival slides or blocks) obtained within one year of screening, or during surgical removal of papilloma(s) will be collected.

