6.11 HPV-6/11 TESTING

Historic HPV-6/11 genotyping results may be used to determine a subject's eligibility for the trial. If historic results are not available, archival tissue collected during previous papilloma removal procedures or biopsy tissue obtained during screening may be used to determine eligibility.

Archival tissue (within 1 year of the screening visit) or biopsy tissue collected at screening, [REDACTED], will undergo HPV-6/11 testing at a central laboratory.

[REDACTED]

[REDACTED]

[REDACTED]

Details of sample collection and shipment information will be provided in the Laboratory Manual.

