8.5.2.2 IMMUNOGENICITY

Increases from baseline in interferon- γ ELISpot and flow response magnitudes will be summarized. The median increases and associated 95% confidence intervals will be calculated.

Changes from baseline in tumor tissue response magnitudes will be summarized.

[REDACTED]

Valid samples for statistical analysis purposes will be those collected within 7 days of the specified visit. Baseline is defined as the last measurement prior to the first treatment administration.

The mITT population will be used for immunogenicity analyses.

Analyses will be summarized and presented by number of prior surgical interventions (≤ 2 , 3-5, and ≥ 6) and overall.

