1.2.3. Study Procedures

The schedule of assessments, as outlined in the study protocol, is provided in [Table 1-1](#).

Table 1-1 Schedule of Assessments

Schedule of Events	Screening	Day 0	Week 3 (±4 days)	Week 6 (±4 days)	Week 9 (±4 days)	Week 11 (±1 week)	Week 26 (±2 week)	Week 52 /End of study (±2 weeks)
Informed consent	X							
Medical history, smoking history	X							
Inclusion/Exclusion criteria	X	X						
Demographics	X							
Concomitant medications, AEs	X	X	X	X	X	X	X	X
Physical exam ^a	X	X	X	X	X		X	X
Vital signs	X	X	X	X	X		X	X
Height, weight, BMI		X	X	X	X			
Safety labs ^b	X	X	X	X	X			
Pregnancy test, if applicable ^c	X	X	X	X	X			
INO-3107		X	X	X	X			
Immunology samples	X	X		X	X	X	X	X
Laryngoscopy and Staging assessment ^e	X ^f			X		X	X	X
Tissue sample ^g	X							X

a. Full physical examination (PE) mandatory at screening and study discharge (Week 52/End of Study visit or relapse), otherwise targeted physical assessment as determined by the Investigator or per subject complaints;

b. Collected within 72 hours prior to dosing such that results are available and assessed against DLT criteria prior to dosing;

c. For women of childbearing potential, a negative serum pregnancy test is required at screening and a negative spot urine pregnancy test is required prior to each study treatment;

e. Staging assessment to be performed during each laryngoscopy and prior to any RRP intervention using the RRP Staging Assessment tool. Video/photographic documentation of laryngoscopy is required.

f. Staging to be performed prior to Routine RRP intervention at Screening, followed by dosing within 14 days.

g. Biopsy tissue should be sent for HPV typing and immunological evaluation at Screening, Week 52, and at any tissue resection, if applicable. Archival tissue collected within 1 year of Day 0 may be sent at screening. Biopsy required with laryngoscopy at Week 52.

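### An archival block 12 to 14 months old may be the only pre-dose sample, and so the baseline, for the descriptive tissue immune endpoint, although papilloma is removed from every subject within 14 days of Day 0

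*Protocol*

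**What the plan says.** **Objective and analysis.** Secondary objective 4 (Protocol 3.3) concerns pro-inflammatory and "immunosuppressive elements in resected tumor tissue at study entry" and at later resections where available. Protocol 8.5.2.2 states: "Changes from baseline in tumor tissue response magnitudes will be summarized". Both Protocol 8.5.2.2 and SAP 3.4 take the final measurement before first dosing as baseline, and neither limits its age. Protocol 6.12 also plans to relate the tissue markers to treatment success.

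**Which tissue may be used.** Papilloma is removed from every subject 0 to 14 days before Day 0 (Protocol 3.0). Tissue from that operation need not be the sample sent. The archival allowance appears with different reference points:

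- Protocol 3.0 (also the synopsis and SAP 1.2.1): "Archival tissue (slides or blocks) obtained within one year of the screening window may be used, or a biopsy conducted during routine surgery".
- Protocol 6.1.1: "Biopsy tissue (archival slides or blocks) obtained within one year of screening, or during surgical removal of papilloma(s) will be collected".
- Protocol 6.11: "Archival tissue (within 1 year of the screening visit) or biopsy tissue collected at screening".
- Schedule of Events footnote (footnote g in SAP 1.2.3, same words in the Protocol): "Archival tissue collected within 1 year of Day 0 may be sent at screening". This footnote covers both HPV typing and immunological evaluation.

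**Sample timing.** Protocol 8.5.2.2 treats samples as valid for analysis only if taken no more than 7 days from the specified visit. The SAP does not repeat that rule; SAP 3.11 tabulates data by the visit recorded on the CRF.

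**The concern.** HPV type can reasonably be read from an older block. An immune profile is a measurement of the lesion at one time. The lesion in an archival block was sampled at an earlier operation, papilloma then persisted or regrew, and the mandatory screening removal followed before the first dose.

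Exclusion criterion 1 bars RRP-directed treatment and "therapy with an experimental agent within 3 months prior to Day 0". Treatment before that point is allowed, so an archival block may come from a period on cidofovir, bevacizumab, chemotherapy or an experimental agent.

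With no control arm, change from baseline is the only visible evidence of a tissue effect. If some baselines are days old and others about a year old, one summary combines intervals of different length and content. The same variation enters any analysis relating the markers to treatment success. No unredacted text flags block age, separates archival from fresh baselines, or deals with surgery or therapy between the block and Day 0.

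**Working it through.** The plan gives no sample size, effect size or interval for the tissue endpoint, so there is no figure to reproduce. The check is date arithmetic.

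**Inputs**

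- Archival look-back: 365 days, counted from screening (Protocol 3.0, 6.1.1, 6.11) or from Day 0 (footnote g).
- Screening length: "The following screening evaluations will be performed within 60 days prior to dosing on Day 0" (Protocol 6.1.1).
- Screening removal: 0 to 14 days before Day 0.
- Week 52 biopsy: 52 × 7 = 364 days after Day 0, window ±14 days.
- Washout: 3 months, about 91 days.

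**Oldest permitted block at Day 0**

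- Counted from screening: 365 + 60 = 425 days, about 14 months.
- Counted from Day 0: 365 days, 12 months.

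**Share of the baseline-to-Week-52 interval that precedes dosing** = age / (age + 364)

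| Baseline tissue | Age at Day 0 (days) | Interval to Week 52 (days) | Share before dosing |
|---|---|---|---|
| Archival, counted from screening | 425 | 789 | 53.9% |
| Archival, counted from Day 0 | 365 | 729 | 50.1% |
| Screening surgery, earliest | 14 | 378 | 3.7% |
| Screening surgery, same day | 0 | 364 | 0% |

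Moving the Week 52 visit to either end of its window changes the archival shares only to 52.9–54.8% and 49.1–51.0%.

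**Part of the look-back not covered by the washout**

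- 425 − 91 = 334 days, 79% of 425.
- 365 − 91 = 274 days, 75% of 365.

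**Intervening surgery.** The screening removal always follows a block from an earlier operation. A block more than a year old at Day 0 also predates both of the interventions that inclusion criterion 4 requires in the year up to Day 0, so at least two operations follow it.

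**Illustration, on assumptions not in the documents.** Suppose a fraction f of subjects have an archival baseline and drift before dosing averages b standard deviations of the change. The mean change is then shifted by f × b. For f from 0.25 to 1 and b from 0.2 to 0.5, this runs from 0.25 × 0.2 = 0.05 to 1 × 0.5 = 0.50 SD. A t-based 95% half-width for a mean is 0.37 SD at n = 30 and 0.55 SD at n = 15. Depending on f and b, the shift could be negligible or as large as the sampling uncertainty.

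**The case against.** **The 7-day rule may already exclude archival blocks.** It stands in the immunogenicity section, after the tissue sentence. If it covers tissue, a months-old block is not a valid sample and the mixing does not arise. But the rule would then cancel the archival allowance in 3.0, 6.1.1 and footnote g. If it does not cover tissue, the old baseline stands. The text needs changing either way.

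**Substitution may be rare.** If screening-surgery tissue is also assayed, the baseline definition selects it. Protocol 6.12 speaks of tissue collected at screening and does not mention archival blocks. This limits the reach, which could be zero subjects. It does not remove the route: 6.1.1 lists archival tissue as an alternative screening sample, and footnote g sends the screening sample for immunological evaluation.

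**Redaction.** Text next to the tissue analysis is blacked out in Protocol 8.5.2.2 and SAP 4.3.2, and the Laboratory Manual is not available. Separate handling of archival tissue may be described there. The visible SAP text names the tissue assessment without a change-from-baseline method, so that method rests on the Protocol.

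**Fresh tissue is not guaranteed.** A reader might infer that a fresh specimen exists for every subject and that archival tissue should simply be barred. The documents support the removal, not the specimen: interventions include laser, only tissue left after genotyping is assessed, and the endpoint applies where tissue is available. That objection stands, and an outright ban could lose subjects from a trial of about 30.

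**Fresh tissue does not isolate a drug effect.** This also stands. Even then the screening removal precedes regrowth, surgery during the trial is allowed, and there is no control arm.

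**Conclusion.** The point holds as a weakness in how the tissue baseline is defined. The documents allow a block 12 to 14 months old to be the immune baseline when it is the only pre-dose tissue assayed. For such a subject about half of the interval to Week 52 (50–54%) precedes dosing, against at most 3.7% with screening-surgery tissue.

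This assumes that the 7-day rule does not cover tissue and that no redacted text handles archival samples separately. The 14-month limit follows only from the wordings tied to screening; footnote g gives 12 months, and the conclusion is the same at either limit.

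A reader might go further and infer that the tissue results as a whole are contaminated, or that they would show a drug effect if only fresh tissue were used. The documents support neither. The number of archival baselines is not given, and a single-arm change remains confounded with fresh tissue.

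The consequence is confined to one descriptive secondary endpoint and the related marker analysis. The primary safety endpoint and the surgery-count endpoint are unaffected.

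**What to change.** 1. In Protocol 3.0, 6.1.1, 6.11, 6.12 and the Schedule footnote, make screening-surgery tissue the immune baseline wherever an assayable specimen exists. Keep archival tissue for HPV typing, or as a fallback only.
2. In Protocol 8.5.2.2 and SAP 3.4 and 4.3.2, base the main tissue-change summary on subjects with screening-surgery tissue. Show archival-baseline subjects separately, listing block date and any surgery or RRP-directed therapy between the block and Day 0.
3. State one archival age limit with one reference date, and say whether the 7-day validity rule applies to tissue. Carry both into the SAP.

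**Cost.** Wording changes, plus preparation and shipping of tissue that is already being removed; no added procedure. The SAP changes can also be applied to subjects already enrolled, provided the collection date of each block is known. The drawback is fewer subjects in the main tissue summary if some have only archival blocks; the separate display keeps their data in view.

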3.1 PRIMARY OBJECTIVE

To evaluate the safety and tolerability of INO-3107 in subjects with HPV-6 and/or HPV-11- associated RRP.

3.2 PRIMARY ENDPOINT

Safety and tolerability as assessed by reported adverse events (AE) and serious adverse events (SAE).

3.3 SECONDARY OBJECTIVE(S)

1. To evaluate the efficacy of INO-3107, as determined by the frequency of RRP surgical interventions in the year following the first dose of investigational product, compared to the frequency in the year prior to Day 0.
2. To evaluate the efficacy of INO-3107 as assessed by changes in the RRP Staging Assessment over time.
3. To evaluate the cellular immune response to INO-3107 when given IM, followed by EP.
4. To evaluate the immunogenicity of INO-3107 as assessed by pro-inflammatory and immunosuppressive elements in resected tumor tissue at study entry and, if available, at subsequent tissue resections.

5. To evaluate any potential association of microRNA (miRNA) profile with decreased frequency of RRP surgical intervention.

3.4 SECONDARY ENDPOINT(S)

1. Number of RRP surgical interventions in the one year following Day 0, compared to the one year prior to Day 0.
2. Changes in Staging Assessment as measured by the RRP Staging Assessment score over time.
3. Antigen-specific cellular immune responses assessed by:
 - IFN- γ secreting cells in peripheral blood mononuclear cells (PBMCs) by ELISpot
 - T cell phenotype and lytic potential in PBMCs by flow cytometry
4. Assessment of pro-inflammatory and immunosuppressive elements in resected tumor tissue, if available.
5. miRNA profile as related to the reduction in frequency of RRP surgical intervention, if possible.

[REDACTED]

- [REDACTED]
- [REDACTED]
- [REDACTED]
- [REDACTED]
- [REDACTED]
- [REDACTED]
- [REDACTED]
- [REDACTED]

[REDACTED]

- [REDACTED]
- [REDACTED]
- [REDACTED]
- [REDACTED]
- [REDACTED]
- [REDACTED]
- [REDACTED]
- [REDACTED]

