 - IFN- γ secreting cells in peripheral blood mononuclear cells (PBMCs) by ELISpot
 - T cell phenotype and lytic potential in PBMCs by flow cytometry
4. Assessment of pro-inflammatory and immunosuppressive elements in resected tumor tissue, if available.
5. miRNA profile as related to the reduction in frequency of RRP surgical intervention, if possible.

Safety Assessment: Subjects will be followed for safety from the time of signing informed consent through Week 52, or the subject's last visit. All adverse events including SAEs, UADEs, DLTs and other AEs will be recorded. Clinically significant changes in laboratory parameters and vital signs from baseline assessments will be assessed.

Efficacy Assessment: A detailed medical history will be obtained for each subject which will include documentation of HPV-6 and/or HPV-11 RRP, a list of RRP surgeries and therapies occurring within 3 years prior to screening, and any periods of remission. Subjects must have had at least two surgical RRP interventions (including laser) in the year prior to and including Day 0, to be eligible for the trial. Subjects must require RRP intervention at the time of entry into this study and will undergo routine surgical removal of their papilloma(s) during screening, within 14 days prior to Day 0 dosing, to maximize standardization of baseline staging across subjects.

The efficacy assessment will be based upon the number of RRP surgical interventions in the 52 weeks post Day 0 compared to the number of RRP surgical interventions in the year prior to Day 0 dosing. RRP surgical interventions include laser therapies. The trial will also evaluate changes in RRP Staging Assessment over time.

Immunogenicity Assessment: The trial will explore [REDACTED] cell mediated immune responses in blood samples taken at baseline (i.e. Screening and Day 0 prior to dosing) and Weeks 6, 9, 11, 26, and 52. Tissue samples will be collected at baseline and if clinically indicated during the study.

[REDACTED]

Clinical Trial Population: Subjects with HPV-6- and/or HPV-11-associated RRP, who require at least two surgical interventions per year for the past year (minimum), for removal of associated papilloma(s). Approximately 30 adult subjects (aged 18 and older) diagnosed with Juvenile-Onset RRP (age at diagnosis <12 years) or Adult-Onset RRP (age at diagnosis ≥12 years) will be enrolled.

Inclusion Criteria; Subjects Must:

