3.7 EFFICACY ASSESSMENT

A detailed medical history will be obtained for each subject which will include documentation of HPV-6 and/or HPV-11 RRP, a list of RRP surgeries and therapies occurring within 3 years prior to screening, and any periods of remission. Subjects must have had at least two surgical RRP interventions (including laser) in the year prior to and including Day 0, to be eligible for the study. Subjects must require RRP intervention at the time of entry into this study and will undergo surgical removal of their papilloma(s) during screening, within 14 days prior to Day 0 dosing, to maximize standardization of baseline staging across subjects.

The efficacy assessment will be based upon the number of RRP surgical interventions in the 52 weeks post Day 0 compared to the number of RRP surgical interventions in

the year prior to Day 0 dosing. RRP surgical interventions include laser therapies. The trial will also evaluate changes in RRP Staging Assessment over time as a secondary endpoint.

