4.0 CLINICAL TRIAL POPULATION

4.1 INCLUSION CRITERIA

1. Provide written IRB-approved informed consent in accordance with institutional guidelines;
2. Be ≥ 18 years of age on the day of signing the informed consent, and able and willing to comply with all trial procedures;
3. Have histologically documented HPV-6- or HPV-11-positive respiratory papilloma or documentation of low-risk positive HPV using a Sponsor approved HPV-6/11 type-specific assay;
4. Have a requirement for frequent RRP intervention in order to remove or resect respiratory papilloma, as defined as at least two RRP surgical (including laser) interventions in the year prior to and including Day 0;
5. Must be appropriate candidate for upcoming surgical intervention per investigator judgement and RRP Staging Assessment score (see [Section 6.4.5](#));
6. Have adequate bone marrow, hepatic, and renal function as defined by: ANC (Absolute Neutrophil Count) ≥ 1000 cells/mm³, platelets $\geq 50,000$ /mm³, hemoglobin ≥ 9 g/dL; concentrations of total serum bilirubin within 1.5 x upper limit of normal (ULN), AST and ALT within 1.5 x ULN, serum creatinine ≤ 1.5 x ULN;
7. Agree that during the trial, male participants will not father a child, and female participants cannot be or become pregnant if they are of child-bearing potential. Subjects must meet one of the below requirements:

- a. Be of non-childbearing potential (≥ 12 months of non-therapy-induced amenorrhea, confirmed by follicle stimulating hormone [FSH], if not on hormone replacement;
- b. Be surgically sterile (vasectomy in males or absence of ovaries and/or uterus in females);
- c. Agree to use one highly effective or combined contraceptive methods that result in a failure rate of $< 1\%$ per year during the treatment period and at least through week 12 after last dose. Periodic abstinence (e.g., calendar, ovulation, symptothermal, or post-ovulation methods) and withdrawal are not acceptable methods of contraception.
- d. Agree to abstinence from penile-vaginal intercourse, when this is the subject's preferred and usual lifestyle.

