Subjects will undergo routine procedure for removal of papilloma(s) during the screening period, however dosing on Day 0 must be performed within 14 days following the procedure. If other eligibility criteria have been confirmed, Day 0 dosing may be performed the same day immediately following the papilloma removal. The following assessments should be noted at the time of the procedure:

- Record vital signs heart rate (HR), respiratory rate (RR), blood pressure (BP) and body temperature ([Section 6.4.2](#));
- Record current concomitant medications/treatments ([Section 6.13](#));
- Collect any new adverse events.

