3.8. Subpopulations

All safety, efficacy, and immunogenicity data will be analyzed separately and combined for subjects by number of prior surgical interventions (≤ 2 , 3-5, and ≥ 6), [REDACTED] and overall.

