4.3.1. Efficacy Analyses

The parameters that follow will be analyzed to support the conclusions of the primary analysis. For categorical endpoints, frequency and percentages will be calculated. For continuous variables, means, medians, or changes in percentage will be summarized. Where appropriate, 95% confidence intervals will be calculated (see specific analysis discussed subsequently). Analyses will be summarized and presented by number of prior surgical interventions (≤ 2 , 3-5, and ≥ 6), [REDACTED] and overall.

.

- Secondary analyses
 - Frequency of RRP surgical interventions in the year following intervention, compared to the frequency in the year prior will be presented as median difference with 95% CI based on non-parametric methodology.
 - Percent reduction in RRP surgical intervention as a categorical variable (categories consist of percent ranges), with frequency and percentages.
 - Change in surgical interval for prior to intervention to post will be presented along with median, mean, and 95% confidence intervals.
 - Change in stage as measured by the RRP Staging Assessment. Median changes and associated 95% confidence intervals will be computed.
 - The relationship of microRNA (miRNA) profiles with frequency of surgical intervention will be described using regression analysis.

■ [REDACTED]

■ [REDACTED]

■ [REDACTED]

In addition to these tabulations, by-subject listings will be provided for all efficacy endpoints.

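### On the stated windows the compulsory screening surgery counts in the pre-treatment year and has no counterpart afterwards, tilting the surgery-count endpoint toward benefit by a model-dependent amount

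*Protocol*

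**What the plan says.** - **Endpoint.** Protocol 3.4 lists first the "Number of RRP surgical interventions in the one year following Day 0, compared to the one year prior to Day 0". The protocol synopsis and Section 3.7 give the two sides as the "number of RRP surgical interventions in the 52 weeks post Day 0" and "the number of RRP surgical interventions in the year prior to Day 0 dosing".
- **Screening (index) surgery.** Protocol 3.7 says that subjects "will undergo surgical removal of their papilloma(s) during screening, within 14 days prior to Day 0 dosing". Section 6.1.1 adds that "Day 0 dosing may be performed the same day immediately following the papilloma removal".
- **Entry rule.** Protocol 4.1 requires frequent intervention, "as defined as at least two RRP surgical (including laser) interventions in the year prior to and including Day 0". The index surgery can therefore be one of the two.
- **After Day 0.** Protocol 3.0 and 6.4.5 allow papilloma removal when the investigator judges it clinically needed; none is compulsory. The compulsory Week 52 procedure is a laryngoscopy with biopsy.
- **Analysis.** SAP 4.3.1 states: "Frequency of RRP surgical interventions in the year following intervention, compared to the frequency in the year prior will be presented as median difference", with a non-parametric 95% CI. It adds categories of percent reduction and a separate analysis of change in surgical interval. SAP Section 5 records the move from mean fold-change to median change.
- **Subgroups.** SAP 3.8 has data "analyzed separately and combined for subjects by number of prior surgical interventions" (≤2, 3-5, ≥6). It does not say over what period the prior surgeries are counted.

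No readable text in either document says how the index surgery is treated in the endpoint count.

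**The concern.** Day 0 is fixed to fall just after an operation. The pre-year then ends with a surgery that every subject has by design, while the post-year starts with the disease just cleared. A patient with a stable condition and an inert treatment would tend to show fewer surgeries afterwards.

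The endpoint is secondary and descriptive, but it is the stated basis of the efficacy assessment. There is no control arm to show what an untreated before/after difference would be. The protocol's summary of changes to Version 3.0 says the data are meant to support Phase 3 planning. A confidence interval for the median difference will be read against zero, and zero is not the no-effect value under this counting.

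**Working it through.** **Inputs.** The windows, the 0-14 day lag, the same-day option and the entry rule of at least two surgeries come from the sections cited above. The plan gives no expected value for this endpoint, so there is no figure to reproduce. It gives only a minimum surgery rate; rates of 2 to 6 per year are an assumption, shown as a range.

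**Step 1: closed form.** Assume no drug effect, surgeries at random (Poisson) with yearly rate L, and same-day dosing. Then pre = 1 + N, where N is kept only if N ≥ 1 (entry rule), and post has mean L.

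E(pre) = 1 + L/(1 - e^-L), so E(pre - post) = 1 + L·e^-L/(1 - e^-L).

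- L = 2: 1 + 2(0.1353)/0.8647 = 1.31
- L = 4: 1 + 4(0.0183)/0.9817 = 1.07

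The leading 1 is the index surgery. The remainder is regression to the mean from the entry rule.

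**Step 2: simulation with lag 0-14 days.** Gaps are Poisson or more regular (gamma shape 4 or 16). The table gives the mean of post minus pre with no drug effect, index surgery counted.

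| Rate per year | 2 | 3 | 4 | 5 | 6 |
|---|---|---|---|---|---|
| Poisson | -1.30 | -1.15 | -1.08 | -1.04 | -1.03 |
| Gamma 4 | -1.01 | -0.90 | -0.86 | -0.82 | -0.79 |
| Gamma 16 | -0.92 | -0.89 | -0.85 | -0.82 | -0.78 |

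The median change is -1 in every cell. If entry is instead driven by consent at a random time in the 60 days before surgery, the mean is -0.62 to -1.21 and the median is still -1.

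**Step 3: what a trial of 30 would show.** Assume rates vary between subjects (mean 3.5 per year, CV 0.5), and take ranks 10 and 21 as the 95% interval for the median (coverage 95.7%). With no drug effect, 62-72% of subjects show a reduction, and the interval lies wholly below 0 in 24-65% of trials. With the index surgery left out, that falls to at most 0.6%.

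**Step 4: percent reduction.** A subject with k other surgeries in the pre-year and k in the post-year shows a reduction of 1/(1 + k): 50% for k = 1, 33% for k = 2, 17% for k = 5. The distortion is largest in subjects with fewest prior surgeries.

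**Step 5: where it shrinks.** Take surgery exactly every 182 days.

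- Index 7 days before dosing: pre has days -7 and -189 (2), post has days 175 and 357 (2). Change 0.
- Index on the dosing day: pre has days 0, -182 and -364 (3), post has days 182 and 364 (2). Change -1.

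Only lags of 0 and 1 day give -1, so the average over lags 0-14 is -2/15 = -0.13. With 3-, 4- or 6-month calendars and timing jitter of SD 7 days or less, the mean is about -0.13 to -0.55 and the median 0. At SD 14 days the median is -1 again. Fixed intervals that do not divide the year (100, 150, 200, 250 or 300 days) give -1 at every lag.

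**Step 6: removing the index surgery.** At 2-6 per year with irregular timing, the null median becomes 0. The mean is -0.30 to +0.22 if the index is dropped from the year ending at Day 0, and about -0.28 to +0.01 if both windows are anchored on the index surgery. The negative part is mainly regression to the mean.

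Anchoring matters. In the 182-day example with a 7-day lag, simply dropping the index gives pre 1, post 2, a change of +1. A 365-day pre-window ending the day before the index runs from day -372 to -8, contains days -371 and -189, and gives a change of 0.

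**The case against.** **The documents do not state that the index surgery is counted.** This stands as a caveat. It is an inference from the windows. For same-day surgery, a year prior to Day 0 is less clear than a year prior to Day 0 dosing, and the entry rule alone says that Day 0 is included. Redactions in Protocol 8.5.2.1, SAP 4.3.1 and SAP Section 5 could hold a rule. But the differing wordings themselves show that a rule is needed.

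**The size is not a known constant.** This also stands. A reader might infer a bias of exactly one surgery per subject. The pilot patients described in Protocol 1.1 had debridement every six months, and Step 5 shows that a near-exact calendar largely removes the bias. In addition, scheduled laryngoscopies at Weeks 6, 11, 26 and 52 might prompt extra removals, and the post-year opens before the four-dose series ends. Both could work the other way, by an unknown amount.

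**Other measures exist.** A reader might take this as the only surgical efficacy measure; it is not. The surgical-interval analysis does not carry the extra count, and by-subject listings would allow recalculation. Neither corrects the reported count or percent reduction.

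**Nothing is tested.** Protocol 8.3 plans no hypothesis test, so a false-positive rate for a signed-rank test would describe an analysis nobody proposes. The planned confidence interval is still affected.

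**The surgery was clinically needed.** True, but the asymmetry comes from placing Day 0 just after it, not from whether it was justified.

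**Conclusion.** The point holds. Following the readable windows, the count comparison and its percent-reduction form favour benefit with no drug effect. With irregular timing at an assumed 2-6 surgeries per year, the null median is -1 and the mean about -0.8 to -1.3. Under a near-exact calendar dividing the year, the mean is about -0.1 to -0.55 and the median 0. Regression to the mean from the entry rule adds a smaller part that recounting does not fully remove.

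This assumes stable disease, no drug effect and no contrary rule in redacted text. It does not show that any observed reduction is wholly artefact.

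A reader might also infer that the subgroups must produce a false gradient. That follows only if they are formed from the same pre-year count, which the documents do not say.

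**What to change.** In SAP 4.3.1 and Section 5:

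1. State that the index (screening) surgery is counted in neither period, including when it falls on the dosing day.
2. Define the pre-window as the 365 days ending the day before the index surgery, and the post-window as an equal length starting after the Day 0 dose. Do not simply subtract one from the year ending at Day 0 (Step 6).
3. Report the median difference and percent reduction on this basis, beside the protocol-defined count labelled as including the index surgery. Base efficacy conclusions on the index-excluded result.
4. State the period behind the ≤2 / 3-5 / ≥6 subgroups. If it is the same pre-year, note that a gradient is expected from regression to the mean.
5. Optionally, compare with earlier years of surgical history as a sensitivity analysis. The summary of changes indicates that this history may be incomplete, so it should not carry the main result.

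The denominator for percent reduction stays at least 1, unless the second qualifying surgery fell between the index surgery and Day 0.

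Cost: SAP wording and one derived variable, with no new data for items 1 to 4. The reported reduction becomes less favourable by up to about one surgery per subject. The analysis of the first 21 subjects, already conducted according to SAP 3.12, needs the same re-derivation.
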